## **7.2 Treatment Assignment and Blinding**

### **7.2.1 Number of Subjects**

Up to 10 healthy adult subjects will be enrolled. All subjects will receive ASN51.

Subjects who withdraw or are removed from the trial after receiving investigational medicinal product (IMP) and prior to completion of the Treatment Period may be replaced on a case-by-case basis, at the discretion of the Sponsor.

### **7.2.2 Method of Assigning Subject Numbers to Treatment Groups**

Subjects will be sequentially assigned a screening identification number upon signing of informed consent. Once eligibility is confirmed (Day 1 of imaging session 1), subjects will receive a 4-digit number on Day 1 before the start of the day's study procedures. Subjects who replace discontinuing subjects who have started procedures/assessments on Day 1 will receive the number of this subject +1000, e.g., subject 2411 will replace subject 1411, subject 2211 will replace subject 1211, etc. The substitute subject will receive the treatment assigned to the withdrawn subject. The following subject numbers are assigned:

Subject numbers 1411 – 1420, replacement subject numbers 2411 – 2420

### **7.2.3 Blinding**

Not applicable

### **7.2.4 Unblinding**

Not applicable

## **7.3 Sites**

ASN51-102 is a single-center study.

## **7.4 Study Duration**

The estimated duration of subject participation for the four parts of the study is as follows:

From Screening (3 weeks) to study conduct to follow-up (3 weeks) to telephone follow-up for potential SAEs (6 weeks): approximately 12 weeks for each subject.

## **7.5 Study Safety Oversight**

### **7.5.1 Safety Review Committee**

The study will be monitored by an SRC. The SRC is intended to ensure that treatment does not pose undue risk to subjects and to determine the individual dose levels to be administered in the study as well as the timing of the PET scans in relation to the time point of the study drug administration. The SRC will review RO data (ASN51-102 study only) and all available PK, safety, and tolerability data at each dose level from the planned, parallel Phase 1 SAD/MAD study ASN51-101 prior to initiating dosing in ASN51-102 and prior to each dose within this study (ASN51-102).

The SRC will be composed of the following core individuals:

- Principal Investigator (PI) or delegate
- Asceneuron SA medical monitor or delegate (must be a physician)

### **7.5.2 Stopping Criteria Based on Urgent Safety Events**

The study (including dose escalation) will be halted if any of the following occur:

[figure not shown]
- One (1) serious adverse event (SAE) that is considered to be at least possibly related to study treatment; or
- Two (2) or more severe non-serious or clinically significant AEs that are considered to be at least possibly related to study treatment irrespective of whether they occur in the same system organ class (SOC) or not.

If following an internal safety review, it is appropriate to restart the trial, a substantial amendment will be submitted to the MHRA and REC. The trial will not restart until the amendment has been approved by the MHRA and REC.

### **7.5.3 Criteria for Dose Level Selection**

Safety and pharmacokinetic data will be assessed by the SRC prior to

- a) The first study drug administration
- b) All subsequent study drug administrations

After each on-treatment PET scan, the SRC will review available RO, PK, safety and tolerability data, before selecting the dose and PET scan timings for the next imaging session.

The SRC may stop dosing at any time if the SRC determines that the next dose would pose an undue risk to subjects.

The safety and PK data will be reviewed by the SRC in an unblinded manner (e.g., with subject identifiers). For each meeting, the Investigator will prepare a report outlining a summary analysis of the safety data of the previous cohort.

## **7.6 Subject Discontinuation**

In accordance with the Declaration of Helsinki, subjects have the right to withdraw from the trial at any time for any reason. The Sponsor must be notified of all subject withdrawals as soon as possible.

### **7.6.1 Removal of Subjects**

The Investigator and Sponsor also have the right to remove subjects from the trial. The Sponsor also reserves the right to discontinue participation of an individual subject.

Subjects may be removed from the trial for the following reasons:

- Occurrence of an AE or SAE that precludes further participation
- Serious adverse event (SAE) considered related to study treatment.

- Any condition that, in the judgment of the Investigator or Sponsor, might place the subject at risk or invalidate the trial
- Pregnancy in subject
- At the request of the subject, Investigator, or Sponsor, for administrative or other reasons
- Protocol deviation or noncompliance
- One or more study drug administrations are missed
- Alanine aminotransferase (ALT)  $\geq 5 \times$  upper limit of normal (ULN).
  - ALT  $\geq 3 \times$  ULN and total bilirubin  $\geq 2 \times$  ULN or international normalised ratio (INR)  $> 1.5$ . (If a subject meets that withdrawal criterion, serum bilirubin fractionation should be performed.)
  - ALT  $\geq 3 \times$  ULN if associated with the appearance or worsening of rash or hepatitis symptoms (fatigue, nausea, vomiting, right upper quadrant pain or tenderness, fever, rash or eosinophilia). Subjects who have -ALT  $\geq 3 \times$  ULN and  $< 5 \times$  ULN, total bilirubin  $< 2 \times$  ULN or INR  $< 1.5$ , who do not exhibit hepatitis symptoms or rash, can continue in the study (and continue receiving trial medication) as long as they can be monitored at least weekly until abnormal results are within the reference range or close to pre-treatment values.

Subjects that experience an AE or SAE as defined above will be followed-up by the Investigator until the AE/SAE has resolved. If a subject discontinues from the trial prematurely, reasonable efforts should be made to perform the Early Termination Visit procedures, within four weeks of discontinuation.

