17. **12-Lead ECG:** During the period of residence, ECGs will be recorded at the timepoints indicated. Assessments will be done at screening visit 1, Day -1 of imaging session 1, and pre-dose on Day 1 in imaging sessions 2 and 3, and at the follow-up visit. Single recordings will be done at all time points. Recordings should be made with subjects in a supine position, after resting for 10 min. Additional unscheduled assessments may be done at the discretion of the Investigator.
18. **PK Sampling:** Plasma samples for assay of the ASN51 will be collected pre-dose and at 0.25, 0.5, 1, 1.5, 2, 3, 4, 6, 8, 12, 16, 24, 36, 48, and 72 h post-dose. Samples scheduled immediately before the PET scan should be taken as close as possible to the planned start of the PET scan samples scheduled for the end of the PET scan should be taken as soon as possible after the PET scan is finished; and samples scheduled during the PET scan should be taken either before or after the PET scan, as close to the scheduled timepoint as possible.
19. Hematology, biochemistry, coagulation, and urinalysis to be taken 72 h post-dose in sessions 2 and 3.
20. **Timing of Assessments:** If more than one assessment is foreseen for a timepoint, PET procedures prevail. All assessments should be staggered in the same order throughout the study with the PK sampling point closest to the scheduled timepoint.

3.0	TABLE OF CONTENTS	
1.0	TITLE PAGE	1
2.0	STUDY SYNOPSIS	4
3.0	TABLE OF CONTENTS	14
4.0	LIST OF ABBREVIATIONS AND DEFINITION OF TERMS	18
5.0	INTRODUCTION AND RATIONALE	21
5.1	Background: O-GlcNAcylation and Protein Aggregation in Neurodegenerative Disease	22
5.2	ASN51 Mechanism of Action and Rationale in Alzheimer's Disease	23
5.3	Nonclinical Studies	25
5.4	Clinical Experience	27
5.5	Summary of Overall Risks and Potential Benefits	27
6.0	OBJECTIVES	28
7.0	INVESTIGATIONAL PLAN	29
7.1	Study Design	29
7.2	Treatment Assignment and Blinding	30
7.2.1	Number of Subjects	30
7.2.2	Method of Assigning Subject Numbers to Treatment Groups	30
7.2.3	Blinding	31
7.2.4	Unblinding	31
7.3	Sites	31
7.4	Study Duration	31
7.5	Study Safety Oversight	31
7.5.1	Safety Review Committee	31
7.5.2	Stopping Criteria Based on Urgent Safety Events	31
7.5.3	Criteria for Dose Level Selection	32
7.6	Subject Discontinuation	32
7.6.1	Removal of Subjects	32
7.6.2	Early Termination Procedure	33

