12.2 Protocol deviations

Before closing the database, data listings will be reviewed to identify any significant deviations and determine whether the data should be excluded from any analysis populations.

Major protocol deviations include subjects who:

- Entered the study even though they did not satisfy the entry criteria.
- Met the criteria for withdrawal from the study but were not withdrawn.
- Received the wrong treatment or incorrect dose.
- Received an excluded concomitant therapy.
- Received investigational product(s) past the expiration date.

In addition, subjects with minor time deviations (measurements taken outside the allowable windows) will be identified. Allowable time windows for pharmacokinetic samples and other procedures are given in HMR Trial Procedures Summary.

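### Protocol 7.6.1: the may-continue sentence says 'or' where 'and' is needed, so two liver-test patterns at ALT 3 to <5 × ULN meet a withdrawal criterion and also qualify for further ASN51

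*Protocol*

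**What the plan says.** Protocol 7.6.1 opens its list with "Subjects may be removed from the trial for the following reasons". One item is ALT at or above 5 × ULN. Below it stands a combined item: ALT of at least 3 × ULN together with either bilirubin of at least 2 × ULN or an INR above 1.5. On this item the protocol adds: "If a subject meets that withdrawal criterion, serum bilirubin fractionation should be performed". It therefore calls the combination a withdrawal criterion in its own words. A further item covers ALT of at least 3 × ULN with rash or hepatitis symptoms.

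That last item ends with a permission for subjects whose ALT lies from 3 to below 5 × ULN. It sets a bilirubin limit of less than twice the ULN, and the wording from that limit onward is: "ULN or INR $< 1.5$ , who do not exhibit hepatitis symptoms or rash, can continue in the study (and continue receiving trial medication". The permission carries one condition, namely "as long as they can be monitored at least weekly until abnormal results are within the reference range or close to pre-treatment values".

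Three other places bear on the point:

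- Protocol Table 1, footnote 19: "Hematology, biochemistry, coagulation, and urinalysis to be taken 72 h post-dose in sessions 2 and 3". Table 1 also schedules these tests on Day -1 of session 3.
- Protocol 7.5.3: "The SRC may stop dosing at any time if the SRC determines that the next dose would pose an undue risk to subjects".
- SAP 12.2 counts among major deviations subjects who "Met the criteria for withdrawal from the study but were not withdrawn".

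**The concern.** The permission is evidently meant for the subjects left over once the withdrawal items have been applied: moderately raised ALT, no symptoms, and neither bilirubin nor INR abnormal. Negating 'bilirubin high **or** INR high' gives 'bilirubin not high **and** INR not high'. The sentence reverses the inequalities but keeps *or*, so a single normal marker satisfies it.

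Read literally, a symptom-free subject with ALT 4 × ULN, bilirubin 3 × ULN and INR 1.0 meets the named withdrawal criterion and may also receive more drug. The situation can arise. Two ASN51 doses are planned 7–14 days apart (protocol 7.1), and chemistry and coagulation results from 72 h after the first dose could be in hand before the second.

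There is a secondary effect on analysis. If such a subject continues, it is unclear whether SAP 12.2 makes that a major deviation. A major deviation is then reviewed for possible exclusion from analysis populations; exclusion is not automatic.

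**Working it through.** No sample size, power or error rate is involved, so the check is a truth table of the two rules.

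**Inputs, all from protocol 7.6.1** (ALT and bilirubin B in multiples of ULN):

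- Withdrawal criterion, W: ALT ≥ 3 and (B ≥ 2 or INR > 1.5).
- May continue as written, C: 3 ≤ ALT < 5, no symptoms or rash, and (B < 2 or INR < 1.5). Weekly monitoring is also required, but it does not depend on B or INR.

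**As written, ALT ≥ 3 and < 5, no symptoms:**

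| Bilirubin | INR | W | C | Result |
|---|---|---|---|---|
| < 2 | < 1.5 | no | yes | continue only |
| < 2 | = 1.5 | no | yes | continue only |
| < 2 | > 1.5 | yes | yes | **both** |
| ≥ 2 | < 1.5 | yes | yes | **both** |
| ≥ 2 | = 1.5 | yes | no | withdraw only |
| ≥ 2 | > 1.5 | yes | no | withdraw only |

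Totals: both 2, continue only 2, withdraw only 2, neither 0. Evaluating at ALT 3.0, 4.0 and 4.9 gives the same pattern.

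**Sensitivity to how W is read.** W could also be parsed as (ALT ≥ 3 and B ≥ 2) or INR > 1.5. For ALT ≥ 3 this classifies all six rows identically, so the overlap does not depend on the parse.

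**Candidate corrections, same six cells:**

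| May-continue condition | Both | Neither | Continue only | Withdraw only |
|---|---|---|---|---|
| B < 2 or INR < 1.5 (current) | 2 | 0 | 2 | 2 |
| B < 2 and INR < 1.5 | 0 | 1 | 1 | 4 |
| B < 2 and INR ≤ 1.5 | 0 | 0 | 2 | 4 |

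The single 'neither' cell in the middle row is B < 2 with INR exactly 1.5. It arises because W uses a strict > 1.5 and the permission a strict < 1.5.

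**The case against.** The strongest reply is that both texts are permissive: subjects *may* be removed and *can* continue, so they are logically compatible and the decision stays with the investigator and sponsor. The intent can also be read from context. That stands as far as it goes: these are not two mandatory orders. But the protocol labels the pattern a withdrawal criterion, the SAP attaches a deviation to not acting on it, and the next item expressly allows dosing in the same pattern. Discretion does not tell the investigator which statement governs.

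Other safeguards reduce the practical risk:

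- Continuation requires at least weekly monitoring.
- The SRC reviews safety before every administration.
- The investigator or sponsor may remove anyone judged at risk.
- Clinically significant laboratory abnormalities must be recorded as AEs (10.4), and AEs can trigger the study halt in 7.5.2.

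None of these removes the overlap. A subject with one abnormal marker can be monitored weekly, and the rest depends on judgement. The public text of 7.5.2 has a missing figure, so the claim is limited to the visible text, where nothing resolves the conflict.

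Rarity also stands. At most 10 healthy subjects enrol, ALT or AST above 1.5 × ULN is excluded at entry, and normally only one further dose is at stake.

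Finally, the overlap is slightly narrower than 'one abnormal marker'. With bilirubin ≥ 2 × ULN and INR exactly 1.5, only the withdrawal criterion applies.

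**Conclusion.** The point holds. The sentence is wrong as written: in two of six bilirubin/INR cells at ALT ≥ 3 and < 5 × ULN without symptoms, a subject meets a named withdrawal criterion and is also allowed further drug. These are logical cells, not event rates. The documents give no rate for such results, and a case is likely to be rare.

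The conclusion rests on the literal wording and on taking the permission as the intended complement of the withdrawal items. It is a conflict in subject-safety guidance with a minor knock-on for deviation classification. It does not bear on the method of the primary PET analysis, and the PET population definition has no deviation clause, although the SAP 12.2 review can consider exclusion from any population. It should be corrected because it concerns the decision to re-dose and the correction is almost free.

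**What to change.** In protocol 7.6.1, make the may-continue condition: total bilirubin < 2 × ULN **and** INR **≤** 1.5. Both changes are needed. Replacing *or* with *and* alone would leave a subject with normal bilirubin and INR exactly 1.5 under neither rule.

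The cost is one word and one sign in one sentence. As a protocol amendment it needs REC/MHRA approval (protocol 13.1 and 13.1.1), so it can be carried with another amendment. Data collection and analysis do not change. SAP 12.2 refers generically to the withdrawal criteria and will follow the corrected protocol without editing.

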### **7.6.2 Early Termination Procedure**

The early termination procedures are noted in the Schedule of Events, in any case the procedures foreseen for the follow-up visit must be completed ([Table 1](#)).

### **7.6.3 Replacement of Subjects**

Subjects who withdraw or are removed from the trial after receiving IMP and prior to completion of the Treatment Period may be replaced on a case-by-case basis, at the discretion of the Sponsor.

## **7.7 Study Completion**

The end of the trial is defined as the date of protocol-specified visit/assessment for the last subject participating in the trial. If the trial ends before all subjects are enrolled because the study objectives have been met, it will not be considered an early study termination.

## 7.8 Scientific Rationale for Study Design

ASN51 is a reversible and substrate competitive inhibitor of O-GlcNAcase that is currently being developed by Asceneuron S.A for the treatment of AD.

The primary objective of this study is to investigate the occupancy of O-GlcNAcase using PET and the O-GlcNAcase ligand [F]-IMA601, and to characterize the relationship between plasma concentration of ASN51 and the occupancy of O-GlcNAcase. These data will serve as a basis for the planning of the dosing and dosing regimen in further clinical studies.

## 8.0 POPULATION

### 8.1 Use of Healthy Young Volunteers

The ASN51-102 study will dose healthy young volunteers (HYVs) for following reasons. HYVs have no confounding pathology or medication use that could interfere with this early phase study, are not expected to have vascular disease that would interfere with arterial cannulation, are unlikely to be taking concomitant medications (e.g., aspirin) that would contraindicate arterial cannulation, are better able to tolerate arterial cannulation, are better suited for obtaining a total of about 600mL of blood for full PK analysis and are better able to tolerate repeated PET scans.

### 8.2 Inclusion/Exclusion Criteria

#### Inclusion Criteria:

Individuals meeting all the following **inclusion criteria** and none of the **exclusion criteria** will be eligible to participate. None of the inclusion criteria are eligible for re-screening. No waivers will be granted and any deviation from below will get recorded as a major protocol deviation. An exception can apply for subjects who meet the inclusion and exclusion criteria, but then miss a cohort that is filled and so they are no longer eligible due to lapse of the 3-week screening window; these subjects may be rescreened.

1. Healthy as determined by the Investigator, based on a medical evaluation including medical history physical examination, neurological examination, laboratory tests and cardiac monitoring.
2. Men or women aged 25-55 years, inclusive (age range was selected on grounds of radiation burden).
3. Women of child-bearing potential with partners of child-bearing potential (see [Section 9.10.7](#) for definitions) must agree to use highly effective contraception (per CTG 2020; bilateral tubal occlusion, hormonal contraception associated with inhibition of ovulation except oral contraception, intra-uterine device with or without intrauterine hormone-releasing system, sexual abstinence in relation to the preferred and usual lifestyle of the subject, ) from at least 28 days before first tracer dosing through 30 days after last dose of IMP. All women of child-bearing potential must have a negative pregnancy test result before administration of test article. Vasectomised partner is also an accepted a highly effective birth control method provided that partner is the sole sexual partner of the WOCBP trial participant and that the vasectomised partner has received medical assessment of the surgical success.
4. Women of non-childbearing potential must be postmenopausal [the last menstrual period was at least 12 months ago, and FSH at screening confirms postmenopausal status], or have no uterus, ovaries, or fallopian tubes). Women who are surgically sterile must provide documentation of the procedure by an operative report or by ultrasound.

5. Non-sterilized male subjects who are not abstinent and intend to be sexually active with a female partner of childbearing potential must use a male condom plus spermicide from 1 day prior to the first tracer administration throughout the total duration of the treatment period and 90 days after the last dose of IMP. Periodic abstinence, the rhythm method, and the withdrawal method are not acceptable methods of contraception. Male subjects should refrain from sperm donation throughout this period.
6. Body weight > 50.0 kg for men and >45.0 kg for women and Body Mass Index within the range 18.5-30.0 kg/m^2 (inclusive).
7. Subjects must understand the nature of the study and must provide signed and dated written informed consent in accordance with local regulations before the conduct of any study-related procedures.
8. Subjects must be, in the opinion of the Investigator, able to participate in all scheduled evaluations, likely to complete all required tests, and likely to be compliant.
9. Subjects must be fluent in the local language.
10. Subjects must agree not to post any personal medical data related to the study or information related to the study on any website or social media site (e.g., Facebook, Twitter, etc.) until the trial has completed.

**Exclusion Criteria:**

Individuals who meet any of the following **exclusion criteria** will not be eligible to participate.

1. A positive urine drug screen/alcohol test at Screening or Day -1.
2. Any history of psychiatric disorders, including substance use disorders, according to the Diagnostic and Statistical Manual of Mental Disorders, 5th Edition (DSM-5) criteria.
3. A diagnosis of intellectual disability (intellectual developmental disorder) or mental retardation.
4. Significant suicide risk as assessed by C-SSRS.
5. A positive Hepatitis B surface antigen or positive Hepatitis C antibody result at Screening.
6. A positive test for human immunodeficiency virus (HIV) antibody at Screening.
7. Alanine aminotransferase or aspartate aminotransferase levels greater than 1.5 times the upper limit of normal (ULN) at Screening or between Screening and first dose of tracer administration.
8. Frequently used any tobacco-containing (e.g., cigar, cigarette, or snuff) or nicotine-containing product (e.g., nicotine chewing gum, nicotine plasters, or other product used for smoking cessation) within 3 months prior to first dose of tracer. Frequent use is defined as 3 or more days per week. Use of any tobacco- or nicotine-containing product is prohibited within 1 week of first dose of tracer.
9. History of regular alcohol consumption within 12 months of the study defined as an average weekly intake of >21 alcoholic units/week for men or >14 alcoholic units/week for women.

10. Regularly consumed (e.g., more days than not) excessive quantities of xanthine-containing beverages (e.g., more than five cups of coffee or the equivalent per day) within 30 days prior to Screening or between Screening and first dose of tracer.
11. Received or used an investigational product (including placebo) or device within the following time period prior to the first tracer dosing day in the current study: 90 days, 5 half-lives or twice the duration of the biological effect of the investigational product (whichever is longer).
12. Other than exceptions outlined in [Section 9.10](#), use of prescription or non-prescription drugs, vitamins, herbal, and dietary supplements (including St John's Wort) within 7 days (or 28 days if the drug is a potential hepatic enzyme inducer) or 5 half-lives (whichever is longer) prior to the first dose of study tracer medication.
13. History of clinically significant sensitivity to any of the study medications, or components thereof or a history of drug or other allergy that, in the opinion of the Investigator or Medical Monitor, contraindicates their participation.
14. Loss of more than 400 mL of blood within 3 months prior to first dose of tracer, i.e., blood donor.
15. A positive serum pregnancy test or lactation.
16. A history or presence of any disease, condition, or surgery likely to affect drug absorption, distribution, metabolism, or excretion. Subjects with a history of cholecystectomy should be excluded.
17. A history or presence of a clinically significant hepatic, renal, gastrointestinal, cardiovascular, endocrine, pulmonary, ophthalmologic, immunologic, hematologic, dermatologic, or neurologic abnormality.
18. A clinically significant abnormality on physical examination, neurological examination, ECG, or laboratory evaluations at screen or between screen and first tracer dose administration.
19. A corrected QT interval measurement corrected according to the Fridericia rule (QTcF)  $> 450$  msec for males,  $470$  msec for females during controlled rest at screen or between screen and first tracer dose administration, or family history of long QT syndrome.
20. Any clinically significant abnormalities in rhythm, conduction, or morphology of the resting ECG and any abnormalities in the 12-lead ECG that, in the judgement of the Investigator or Medical Monitor, may interfere with the interpretation of QTc interval changes, including abnormal ST-T-wave morphology or left ventricular hypertrophy.
21. PR (PQ) interval shortening  $< 120$  msec (PR  $< 120$  msec but  $> 110$  msec is acceptable if there is no evidence of ventricular pre-excitation).
22. PR (PQ) interval prolongation ( $> 220$  msec), intermittent second- (Wenckebach block while asleep or in deep rest is not exclusionary) or third-degree AV block.
23. Persistent or intermittent complete bundle branch block (BBB), incomplete bundle branch block (IBBB), or intraventricular conduction delay (IVCD) with QRS  $> 120$  msec.

24. A clinically significant vital signs abnormality at screening or between screening and first tracer dose administration. This includes, but is not limited to, 3 measurements (each 5 minutes apart) in the seated position: (a) systolic blood pressure < 90 or > 140 mmHg, (b) diastolic blood pressure < 50 or > 95 mmHg, or (c) heart rate < 45 or > 100 beats per minute. The average of the 3 measurements should be used to assess eligibility.
25. Significant (> 10%) weight loss or gain within 30 days prior to Screening and first tracer dose administration.
26. A history of seizure. History of a single benign febrile convulsion of childhood is permitted.
27. A history of head trauma, including closed head injury with loss of consciousness.
28. A history of symptomatic orthostatic hypotension (i.e., postural syncope)
29. A history of neuroleptic malignant syndrome.
30. A history of chronic urinary tract infections.
31. The subject is, in the opinion of the Investigator or Medical Monitor, unlikely to comply with the protocol or is unsuitable for any reason.
32. Currently employed by Asceneuron SA or by a clinical trial site participating in this study, or a first-degree relative of an Asceneuron SA employee or of an employee at a participating clinical trial site.
33. Unsatisfactory venous access
34. Significant exposure to ionising radiation as part of research (defined as ICRP category IIb or above: no more than 10 mSv in addition to natural background radiation including this trial), within the previous 12 months prior to first tracer dose administration.
35. Unsuitable or unwilling to undergo the imaging procedures, as determined by an MRI safety questionnaire. Reasons for exclusion include but are not limited to presence of a cardiac pacemaker or other implanted electronic device; ferromagnetic metal foreign bodies, intracranial aneurysm clips or other metallic objects; non-MRI compatible heart valves; inner ear implants; or a history of claustrophobia.
36. Significant structural brain abnormality, as determined by MRI.
37. Contraindication for arterial cannulation: Allen's test indicating potential risk in placement of the arterial cannula.
38. Subjects with a COVID-19 vaccination within two weeks of screening or due to receive second dose of COVID-19 vaccine while participating in the study.

